14.7. Preliminary analyses

14.7.1. Baseline comparisons

Analyses are performed using the baseline data to compare the two study conditions with respect to demographic characteristics and important prognostic factors. The 6th grade data have the same hierarchical structure as the 8th grade data, because both involve observations taken from girls nested within schools which are in turn nested within the cells defined by the Field Center x condition interaction. As a result, we can expect the same kind of correlated data at baseline that we expect at the end of the study, and the methods used for baseline comparisons need to reflect that correlation. For variables distributed Gaussian, we propose the same kind of two-stage analysis described above for the primary analysis. The first-stage analysis is based on the General Linear Model and is appropriate for endpoints that are related to one or more fixed-effect independent variables when all remaining variation is appropriately allocated to a single residual error that has a Gaussian distribution (Searle, 1971). Many variables of interest at baseline have other distributions, such as data from dichotomous variables (e.g., gender) or data representing counts (e.g., servings of fruits and vegetables). For these variables, we propose variations of the first-stage analysis based on the Generalized Linear Model (McCullagh, 1989), which allow us to specify a binomial error distribution and logit link, as is appropriate for dichotomous variables, or a Poisson error distribution and log link, as is appropriate for count variables.

The results of these analyses allow us to characterize the similarities and differences between the two study conditions at baseline. Given random assignment from within Field Centers of 18 schools to each of two conditions, we do not anticipate substantial differences between the two conditions at baseline, though it is important to look for them so that we can avoid potential confounding in the primary analysis.

14.7.2. Interim analyses

The benefits of the intervention, while significant in a public health context, are expected to be modest in terms of the clinical impact on any single girl. Moreover, the risk to girls in the control schools from not obtaining an effective intervention are considered to be minimal over the period of the study. As a result, we do not plan to collect or analyze interim data for primary or secondary endpoints.

15. ADVERSE OUTCOMES AND SAFETY

15.1. Background and rationale

Protection of study participants from risks related to the study is a major concern to investigators and institutions participating in TAAG. Each institution must seek site-specific Institutional Review Board approval for TAAG. A signed and dated statement that the protocol and informed consent form have been approved by an Institutional Review Board is forwarded to the Coordinating Center and archived.

15.2. Monitoring physical activity-related injuries

NIH guidelines indicate that an adverse event is "any untoward medical occurrence in a study participant." A serious adverse event is "any event that is life-threatening, requires an inpatient hospitalization, results in significant disability, results in congenital anomaly, results in death, requires intervention to prevent impairment or damage, or is an otherwise important medical event." In TAAG, an adverse event is operationally defined as "an event that causes bodily or psychological damage and that requires either treatment by medical personnel or causes the student to miss school" (Anderson, 1994). TAAG encourages changes in physical activity. Although unlikely, these changes could lead conceivably to adverse effects. Adverse events are monitored in all girls attending TAAG intervention and control schools. Since boys are exposed to certain aspects of the TAAG intervention (e.g., physical education classes in some schools), they are included in monitoring procedures when feasible.

An increase in time spent in physical activity at school and out of school could lead to an increase in the number of injuries. This is probably the most common event that might be considered an adverse effect; in rare cases, children may suffer injuries that are debilitating or fatal. Each school will have a procedure for recording and reporting any injury resulting from physical activity during participation in school-sponsored activities. A copy of this log is kept at the school, at the site TAAG offices, and at the Coordinating Center. A log, to be completed by physical activity program personnel, monitors adverse events among participants in TAAG-sponsored after-school or weekend physical activity programs. The adverse events reporting scheme is outlined in Figure 15.1.

Specific possible injuries include strains, tears, or fractures (Surgeon General Report on Physical Activity and Health, 1996). Adolescents with developing bodies are at risk of permanent physical damage if injury occurs to the growth plates of long bones or to other connective tissue structures. Most musculoskeletal injuries related to physical activity can be prevented by gradually working up to the desired level of activity. The specific type of injury is recorded on the adverse events logs described above and reported to the Coordinating Center.

Severe exertion in hot, humid conditions can cause electrolyte imbalance or dehydration. Timely fluid intake and replacement can prevent or ameliorate such conditions. Regular physical activity can improve cardiorespiratory fitness and reduce

the risk of cardiovascular disease mortality over the long term. Over the short term, sudden cardiac deaths, while possible, are very unlikely in this age group.

Another category of potential adverse effects would be disorders of eating behaviors that result from increased attention to physical activity, fitness, and weight. Among the conceivable adverse effects are binge eating, bulimia, and anorexia. Other potential adverse effects are difficult to predict; they might include the possibility of psychological problems stemming from increased attention to health, fitness, or weight. The difficulties of attribution and the *a priori* low expectation of these problems developing due to the TAAG interventions argue against surveillance for these conditions.

15.3. Procedures for monitoring adverse events

Four procedures are used to monitor adverse events in girls attending TAAG middle schools:

- 1. A form, to be completed by measurement staff, records adverse events and serious adverse events reported by each girl upon her completion of the measurement procedures.
- 2. A form, to be completed by TAAG staff, monitors serious adverse events occurring in both girls and boys on school grounds or during participation in school-sponsored activities.
- 3. A student recall survey, to be completed by girls completing the measurement protocol, captures serious adverse events occurring among participants in TAAG-generated after-school or weekend physical activity programs in intervention catchment areas.
- 4. A log, to be provided by school personnel, records all missed days in TAAG schools.

The flowchart in Figure 15.1 was adapted from that provided by the NHLBI and describes the reporting flow for both Adverse Events and Serious Adverse Events. One person in each measurement team is designated as the person who assumes responsibility for all adverse events reporting associated with measurement activities (Measurement Adverse Events Coordinator).

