1.14. Adverse outcomes and safety monitoring

Potential intervention-related risks include musculoskeletal injuries and electrolyte imbalance or dehydration as a result of physical activity in hot, humid weather. Others that are very unlikely include reduction in growth due to negative energy balance, sudden death or psychological problems such as disorders of eating, which may be the result of increased attention to physical activity, fitness, and weight. Adverse events are monitored at baseline and follow-up using forms, logs and school records. Serious adverse events, defined as "any event that is life-threatening, requires an inpatient hospitalization, results in significant disability, congenital anomaly, or death, requires intervention to prevent impairment or damage, or is an otherwise important medical event," are reported to the Principal Investigators and their Institutional Review Boards,

the Coordinating Center, the NHLBI, and the Data and Safety Monitoring Board (DSMB).

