TAAG Programs for Physical Activity	Provide and promote a variety of accessible, safe and fun physical activity programs and opportunities during the school day, after school, on the weekends and in the summers, with multiple options available at all times. Provide a minimum of 30 minutes MVPA per day in TAAG sponsored and/or promoted physical activity programs. Work to advance school-wide change, including policy change, that promotes and supports physical activity.	 Develop and maintain school, community, and university partnerships that work to: increase the number of available programs involving physical activity in schools and the community (including developing new programs and enhancing existing programs) improve access and reduce barriers to program participation promote attendance and reinforce participation in programs and activities 	Partnership Materials/Resource Manuals Manual of Operations	Committed partners from school and community with Field Center facilitator	P1-3 S1-3 A1-A5

* P1 – P3 are the objectives for the Physical Environment
 S1 – S3 are the objectives for the Social Environment
 A1 – A5 are the objectives for Adolescent Girls

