7.3.4. Programs for physical activity

The TAAG Programs for Physical Activity component draws from Organizational Change Theory and direct action community organizing in developing a process by which schools, communities, and the TAAG intervention staff form partnerships to accomplish a common goal of increasing girls' participation in physical activity at school and outside of the regular school day. A unique aspect of this partnership is that it school-based rather than state or other community-institution-based. It may be argued that using the school as the hub of the partnership limits its scope and reach. However, since schools are the primary institutions in the community that focus on youth needs, and since schools are relatively stable institutions with a constant mission, we believe that this model has great potential to be effective in resulting in more physical opportunities for girls locally and may serve as the impetus for wider community change that expands beyond the local school. School district or state-level policy change (i.e., district or state-level requirements for daily PE, state or district level funding for transportation or programming) may occur as a result as the demonstrated successes of the school-based activity partnerships. The objectives for the TAAG Programs for Physical Activity are to:1) provide and promote physical activity programs during the school day, after school, on the weekends, and during the summer in both school and community-based venues; 2) provide a minimum of 30 minutes of MVPA during each program period of TAAG-sponsored activities; and 3) work to advance school-wide change including policy change, that promotes and supports physical activity.

Programs for Physical Activity intervention strategies:

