The Programs for Physical Activity process begins immediately after randomization with a goal of having programming begin by the fall of the first year of the intervention either through Jump-Start Activities or in conjunction with activities implemented as a result of the partnership decisions. The number of programs is anticipated to grow rapidly during the first year and by the second year of the intervention daily programs or opportunities can be identified that are a result of the Programs for Physical Activity. Programming is anticipated to occur during the summer between the first and second year of the intervention. We start the partnership development by compiling formative assessment information from the school, community agencies, girls, and parents and by conducting one-on-one interviews in the community. One-on-one interviews are conducted by TAAG intervention staff with a variety of stakeholders in the community (e.g., school personnel, community agency personnel, private business owners, and parents) to hear their perspectives on the issue and to assess their interest and potential commitment to being involved in the partnership.

The TAAG Field Center interventionist compiles information gathered from the formative assessment and the one-on-one interviews into a Summary Report. This is a brief overview of current physical activity opportunities in the school and community for use in educating and motivating potential partners. A first meeting of the potential partners (identified through formative assessment and one-on-ones) is convened. At a minimum, one school, community, and a TAAG intervention staff member make up the initial Planning committee. Other interested stakeholders may be involved as programming objectives are set and operationalized. The Summary Report is shared and other stakeholders are identified.

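### The two program-specific adverse-event instruments name only after-school or weekend programs and leave out the planned summer programs

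*Protocol*

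**What the plan says.** Section 15.2 describes a log, kept by program personnel, that "monitors adverse events among participants in TAAG-sponsored after-school or weekend physical activity programs". Section 15.3 item 3 adds a recall survey, completed by girls who finish the measurement protocol, that "captures serious adverse events occurring among participants in TAAG-generated after-school or weekend physical activity programs in intervention catchment areas". Chapter 15 does not mention summer.

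The intervention chapter treats summer as a category of its own. The first objective of Programs for Physical Activity in 7.3.4 is to "provide and promote physical activity programs during the school day, after school, on the weekends, and during the summer", in school and community venues. Table 7.2 lists the times of delivery as "during the school day, after school, on the weekends and in the summers". On timing, 7.3.4 says: "Programming is anticipated to occur during the summer between the first and second year of the intervention". Section 7.2.3 also names summer activities, and the sample school memorandum (part I, item 7) provides stipends for staff who supervise TAAG activities after school or in summer.

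Section 1.14 names among the possible intervention risks "musculoskeletal injuries and electrolyte imbalance or dehydration as a result of physical activity in hot, humid weather". Section 15.2 defines an adverse event operationally as one that causes bodily or psychological damage and that "requires either treatment by medical personnel or causes the student to miss school".

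**The concern.** A program leader or Field Center works from the scope printed on the instrument. As written, the leader of a TAAG-sponsored summer class at a community agency has no stated duty to keep the log, and a girl filling in the recall survey is not asked about that class. Section 15.2 undertakes to monitor adverse events in all girls at study schools, and activity in hot, humid weather is a risk the protocol itself names. If planned programs sit outside the instruments designed for programs, safety information on that part of the intervention depends on routes designed for other settings. A low count from summer would then be hard to interpret.

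**Working it through.** No arithmetic applies. The check sets the scope of each reporting route against one case: a non-serious injury at a TAAG-sponsored summer program held at a community agency.

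| Route | Scope as written | Reaches the case? |
|---|---|---|
| Program-personnel log (15.2) | Adverse events; TAAG-sponsored after-school or weekend programs | Not as worded |
| Recall survey (15.3 item 3) | Serious events only; measured girls only; after-school or weekend programs | No |
| Measurement-staff form (15.3 item 1) | Adverse and serious events a girl reports on finishing measurement | Only if she is measured and recalls it |
| Staff form (15.3 item 2) | Serious events only; school grounds or school-sponsored activities; no season limit | No |
| Missed-days log (15.3 item 4) | School absences | No; there are none while school is out |
| School injury procedures (5.1 item 2, 15.2, memorandum part II item 7) | School-sponsored activities, and school grounds in 5.1 and the memorandum; no season limit | No, unless the program is school-sponsored |
| Partner-agency procedure (5.4) | Acute injuries or emergencies in TAAG-sponsored activities; no season limit | Possibly, if acute |

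Four steps follow.

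1. Of the two instruments written for TAAG programs (the first two rows), both omit summer: 2 of 2.
2. The measurement-staff form is a weak substitute. The memorandum places the intervention in the 2003-04 and 2004-05 school years, so the summer named in 7.3.4 is that of 2004. The next measurement round starts on 1/1/05 (section 4.5), months later, and section 15.3 states no recall period.
3. The partner-agency procedure is the one route that clearly extends to the case. In 5.4 it is something agencies should have or be willing to develop, whereas the emergency-response protocol in the same section is a must. Nothing in the text of 15.2 or 15.3 says which instrument receives such a report.
4. The definition has two alternative criteria besides damage: medical treatment or missed school. While school is out only the first can be met. An untreated injury that would have kept a girl out of class counts in term but not in summer, wherever the program is held.

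A related point is that the 15.2 log is not among the four procedures listed in 15.3, so the two sections do not give one consistent list of instruments.

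**The case against.** The strongest reply is that after-school is the protocol's loose name for the whole component. Section 11.3.3 describes the component's objective as after-school and weekend programs although 7.3.4 includes summer, section 13.2 speaks of registering after-school programs, and section 16.2 attaches the same label to the working group. The chapter 15 phrase may therefore be shorthand and not an intended exclusion. Figure 15.1, the reporting scheme, is not shown and may add detail. This part stands as a doubt about intent. It does not settle scope, because the intervention text repeatedly lists summer apart from after-school and weekend, and staff follow the wording they are given.

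A reader might go further and infer that summer programs are wholly unmonitored, or that the monitoring board would see no heat-related events because none were collected. The documents do not support that. Section 7.3.4 places programs in "after school, on the weekends, and during the summer in both school and community-based venues", so serious events at summer programs on school grounds fall under 15.3 item 2. Section 5.4 covers acute injuries in any TAAG-sponsored activity, and 1.14 sends serious adverse events to the investigators, review boards, NHLBI and the board without a seasonal exception. The definition of a serious event has no missed-school criterion. Nor does the protocol say that summer is the season of greatest risk; it speaks of hot, humid conditions, and the season is an inference.

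**Conclusion.** The mismatch between chapter 15 and section 7.3.4 is real and the passages should be reconciled. It is a gap in systematic capture, widest for non-serious events at community-based summer programs, and the missed-school criterion adds to it during the break. Its size can be stated only as scope: both program-specific instruments omit summer, and one of the two alternative criteria in the definition cannot operate. The number of events or the share of exposure affected cannot be given, since summer programming is anticipated with no volume stated.

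The conclusion rests on reading the scope phrases as written and on the text of chapter 15 without Figure 15.1. The primary analysis is not affected. The change is worth making because it concerns safety data and costs little.

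**What to change.** - In 15.2 and in 15.3 item 3, state the scope as all TAAG-sponsored (TAAG-generated) programs, including those held in summer, and list the program-personnel log among the procedures in 15.3.
- Have leaders of summer programs complete the existing log.
- State that reports received from partner agencies under 5.4 are entered on that log.
- Add to the operational adverse-event definition an equivalent to missing school for periods when school is not in session, with the wording left to the investigators and the monitoring board.

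The scope should stay with programs TAAG sponsors or generates. Reaching out to existing third-party programs that TAAG only promotes would be a larger undertaking and is not needed here. No new heat-illness code is asked for, since 15.2 already records the specific type of injury on the logs. The cost is a few lines of text and the time summer leaders spend on a form already in use.

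### Protocol 15.2 and 15.3 conflict on which injuries are recorded and with what tool, and injury outside school-sponsored activity cannot be compared between arms

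*Protocol*

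**What the plan says.** Section 15.2 sets a broad scope. On population: "Adverse events are monitored in all girls attending TAAG intervention and control schools". On the expected harm: "An increase in time spent in physical activity at school and out of school could lead to an increase in the number of injuries". The study's own definition of an adverse event does not require seriousness; it covers bodily or psychological damage that "requires either treatment by medical personnel or causes the student to miss school".

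Section 15.2 then describes two logs. For school settings: "Each school will have a procedure for recording and reporting any injury resulting from physical activity during participation in school-sponsored activities", and "A copy of this log is kept at the school, at the site TAAG offices, and at the Coordinating Center". For TAAG-sponsored after-school or weekend programs, program personnel keep a log of adverse events.

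Section 15.3 lists four procedures:

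- Item 1 is a form on which measurement staff record adverse and serious adverse events reported by each girl when she finishes measurement.
- Item 2 is a form completed by TAAG staff that "monitors serious adverse events occurring in both girls and boys on school grounds" or in school-sponsored activities.
- Item 3 is a recall survey of measured girls that "captures serious adverse events occurring among participants in TAAG-generated after-school or weekend physical activity programs in intervention catchment areas".
- Item 4 is a school log of all missed days, with no cause stated.

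Other sections add reporting duties. Section 5.1 (criterion 2) and the sample school memorandum in Appendix 3 (item 7 of the duties for all schools) make every school, control schools included, report acute activity-related injuries on school grounds or in school-sponsored activities. Section 5.4 places a similar expectation on partner agencies, for TAAG-sponsored activities.

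**The concern.** Two things do not fit.

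First, the sections describe different data collection for the same settings. Staff working from 15.2 would log non-serious injuries. Staff working from items 2 and 3 of 15.3 would not, and for TAAG programs they would also use a different instrument and a different reporter.

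Second, 15.2 promises monitoring of all girls in both arms and names out-of-school activity as one route to more injuries. Yet the dedicated tools outside school sponsorship follow TAAG programs only, and those exist only in the intervention arm.

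At stake is the ability of the monitoring board (section 16.3) to judge the harm that 15.2 calls probably the most common. If 15.3 is followed literally, events meeting the study's own definition go unrecorded by items 2 and 3, and program events are counted in one arm with no reference rate. The setting matters: section 2.6 places most youth activity outside the classroom, and the community-linked programs are the trial's signature feature (section 7.3).

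**Working it through.** No arithmetic reproduces or tests a figure here, because the protocol gives no injury rate, safety sample size or safety power. The check is to set the sections side by side by setting.

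| Setting | 15.2 and related sections | 15.3 | Arms | Result |
|---|---|---|---|---|
| School grounds and school-sponsored activity | Log of any injury in school-sponsored activity; reporting of acute injuries (5.1, Appendix 3) | Item 2: serious events only | Both | Severity conflict |
| TAAG after-school or weekend programs | Personnel log of adverse events; partner-agency reporting (5.4) | Item 3: student recall, serious events only | Intervention only | Conflict on severity, instrument and reporter |
| Activity neither school-sponsored nor in a TAAG program | No dedicated tool | No dedicated tool | Neither | Gap |
| Completion of measurement | – | Item 1: adverse and serious events, each measured girl | Both | Available, scope unclear |
| Missed school days | Part of the adverse-event definition | Item 4: all missed days, no cause | Both | Available, not attributable to injury |

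**Severity.** Take a muscle strain that is treated by medical personnel and is not serious. It meets the 15.2 definition. If it happens in intramural sport, it enters the 15.2 school log but not item 2. If it happens in a TAAG weekend program, it enters the 15.2 program log but not item 3. Strains are among the injuries that 15.2 itself lists.

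**Between-arm comparison.** Suppose the same strain happens in a community league that is neither school-sponsored nor linked to TAAG. No dedicated tool records it in either arm. Item 4 would show a missed day, if there was one, without the reason. Item 1 might pick it up, but its reach is unclear: it is tied to the end of measurement, and the coordinator named in 15.3 handles events connected with measurement activities.

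**Item 3 count.** By design, item 3 contributes 0 events from the 18 control schools. An item 3 difference between arms is therefore the intervention-arm count minus 0, which equals the intervention-arm count whatever the true effect on injury. It would show an excess if even one event occurred, and it gives no reference rate against which to judge a real excess.

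**The case against.** The strongest defence is that 15.2 and 15.3 complement each other. Nothing in 15.3 cancels the 15.2 logs, section 1.14 speaks of monitoring by forms, logs and school records, and Figure 15.1, which is not shown, may tie the pieces together. Item 3 can be read as surveillance of the programs TAAG itself creates, and no section plans a between-arm count of its events. The protocol also regards adverse effects as unlikely.

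Much of this limits the point. Three stronger readings that a reader might infer are not supported:

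- That no excess of injuries could be detected. The 15.2 school log and the duties in 5.1 and Appendix 3 capture non-serious injuries in both arms for school-sponsored activity. That includes much after-school sport: section 6.2.3 reports that most schools offer interscholastic and intramural programs, usually after school. Missed days are also logged in both arms.
- That 15.3 records serious events only. This is true of items 2 and 3 but not of items 1 and 4.
- That control girls are never asked about injuries outside school. Item 1, read broadly, could ask them, though only measured girls and only at measurement times.

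What the defence does not remove is the text itself. Section 15.3 presents four procedures, neither 15.2 log is clearly one of them, and the severity thresholds differ. Under the complementary reading, there is still no dedicated capture, in either arm, of activity that is neither school-sponsored nor in a TAAG program. The missing figure supports neither side.

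**Conclusion.** The point holds in two parts. Sections 15.2 and 15.3 contradict each other on severity in both school and TAAG-program settings, and on instrument and reporter in TAAG programs; they must be reconciled. Separately, injury outside school-sponsored activity cannot be compared between arms, which does not fit the stated monitoring of all girls in intervention and control schools.

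In size, item 3 ascertainment is nil in 18 of the 36 schools, and other activity outside school sponsorship has no dedicated tool in any of the 36. The number of events missed cannot be estimated without an injury rate. The second part rests on item 1 not being a full both-arm injury inquiry, which its wording leaves open. A broad reading would narrow the gap for measured girls without closing it. A claim that a planned analysis is biased against the intervention would go too far, since no between-arm count of these events is specified; the risk arises only if one is made.

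**What to change.** 1. List the two 15.2 logs among the procedures in 15.3, and apply the 15.2 adverse-event definition to items 2 and 3, with serious events flagged within them.
2. Give the item 3 recall question to all measured girls in both arms. Word it for any after-school or weekend physical activity, and include a flag for TAAG programs.
3. Report these rates by arm to the monitoring board. Tabulate events captured only through TAAG-program tools separately, outside between-arm counts.

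The cost is one short recall item in control schools, where girls already complete measurement, and more non-serious events to tabulate. No new staff or procedure is needed. Section 11.3.5 already sets the pattern: its exposure questions go to all girls in follow-up measurement so that the intervention can be separated from secular trends.
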